For group analysis, the 3-D anatomical datasets of each subject will be spatially normalized and converted to the standard anatomical space. The resulting normalization parameters will be applied to the 4-D time series datasets. To estimate the main effect of a task per group, the group analysis will be carried out using a three-way analysis of variance (ANOVA) with subject as a random factor and the task and group as fixed factors ($p \leq 0.025$, voxelwise corrected) to identify (1) shared abnormalities in all patients vs. controls, and (2) distinct abnormalities between SD vs. SD/VT patients. Statistical differences in brain activation extent will be assessed using the subtraction method within the three-way ANOVA design. This univariate data analysis will provide information about the extent and intensity of brain activation in different groups (i.e., SD and SD/VT patients vs. controls and SD patients vs. SD/VT patients).

To further our knowledge of functional brain abnormalities in SD and VT, we will perform multi-stage brain network analysis, which will allow for identification of abnormal brain networks and the relationship between the key network regions, possibly contributing to the pathophysiology of these disorders. For this, we will first perform a correlation analysis between functional and structural datasets in SD and SD/VT patients to determine the brain regions of abnormal function with underlying structural changes. The structural data will be derived from the *Studies 1.3.2 and 1.3.3*.

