Sodium oxybate was administered in the office by mouth. Pre- and one hour post-drug voice and speech examinations were performed and videotaped. Initial dose was 1 gm three times daily. It was increased individually every two weeks, until a dose was achieved that improved symptoms without undesirable side effects. The target dose was 1.25 gm T.I.D., although the dose required to achieve benefits varied between patients and correlated with the dose of alcohol required to achieve a similar result. Sodium oxybate was well tolerated by all patients without tolerance and rebound. Based on blinded acoustical analysis of voice and speech samples, SD-related symptoms (breaks, harshness and breathiness) improved over 36% from baseline, whereas voice tremor improved over 71% from baseline. Some patients continued sodium oxybate treatment together

with botulinum toxin injections after study completion. These patients reported that such combined use helped prolong the botulinum toxin injection cycle in addition to relieving VT symptoms.

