2.3 Research Design

The following 2 groups of patients will participate in the proposed studies of Specific Aim #2: (1) SD patients, and (2) SD/VT patients. Because sodium oxybate has been shown to be effective in patients with movement disorders who self-report symptom improvement after alcohol intake, only ethanol-responsive patients will be recruited for the purposes of these studies. We estimate that 60% of ethanol-responsive patients per group, who participated in the studies in Specific Aim #1, will also participate in the studies in Specific Aim #2. Both ADSD and ABSD patients will be included and closely matched with ADSD/VT and ABSD/VT patients. Patients will be identified according to the screening and detailed examinations as described in Specific Aim #1. In this Specific Aim, we will (1) evaluate the central effects of sodium oxybate in SD and SD/VT patients to determine the relationship between improved clinical symptoms and modulated brain function, and (2) examine the extent of central effects from the combined use of sodium oxybate and botulinum toxin treatments as an alternative treatment schedule for patients with limited benefits.

2.3.1 Study #1: Mapping central effects of sodium oxybate treatment in patients with SD and SD/VT using fMRI during symptomatic speech production. Similar to the fMRI study under Specific Aim #1, we will use a sparse-

sampling event-related BOLD fMRI design during symptomatic voice and speech production on a 3.0 Tesla Philips MRI scanner. Each patient will participate in 2 fMRI sessions, before and after treatment with sodium oxybate. All recruited patients will have to be symptomatic; if they are treated with botulinum toxin injections, they may be included only if they are symptomatic at the end of their botulinum toxin treatment cycle. During each scanning session, the patient will be asked to perform short English sentences as well as repetitive and continuous vowel /i/, designed to elicit SD and VT symptoms. Four scanning sessions will be acquired with a total of 36 experimental trials and 24 baseline resting conditions. Structural MRI will be acquired for an anatomical reference.

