Following the initial (baseline) fMRI session, patients will receive an individualized tolerable and efficacious single dose of sodium oxybate, given orally in the office. Patients' symptoms will be evaluated and videotaped one hour after receiving this dose with the immediately followed-up second fMRI session, during which the patients will be asked to produce the same tasks performed during the pre-treatment fMRI study. Patients' post-treatment scans will be compared to their pre-treatment scans to identify differences in brain activation abnormalities due to the effects of sodium oxybate treatment. Voice and speech production during both scanning sessions will be digitally recorded for acoustical analysis and correlations with the central effects of the treatment.

Data analysis. Using AFNI software, fMRI data analysis will include initial pre-processing followed by analysis of the task-related responses using multiple linear regression with a single regressor for each task convolved with a canonical hemodynamic response function, as described above in *1.3.1 Study of Specific Aim #1*. For group analysis, a two-way ANOVA will be conducted with subject as a random factor and task as fixed factor (corrected $p \leq 0.025$). Conjunction analysis at a cluster significance threshold of $p < 0.005$ will determine common and distinct regions of activation within the patient group during task production in the pre- and post-treatment fMRI sessions. Finally, pre- and post-treatment neuroimaging findings will be correlated with the behavioral data derived from acoustical analysis of voice and speech recordings.

Additionally, to determine the extent of sodium oxybate effects on speech network dynamics, we will re-examine functional and effective network connectivity using the same PPI and DCM procedures as described in the *Study 1.3.1*.

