a. **Human Subjects Involvement, Characteristics, and Design.** As described in the *Approach* section, we will recruit SD, SD/VT and healthy control subjects for participation in the proposed studies. Both ADSD and ABSD patients as well as ADSD/VT and ABSD/VT patients will be included and matched with each other in their age, gender and SD type (AD or AB). Clinically healthy subjects will be those who do not have present or past history of any neurological, psychiatric or laryngological problems. Controls will be carefully matched with SD and SD/VT populations by their age, gender, and ethnicity.

For all studies in Specific Aim #1, we propose to recruit the same 20 subjects per SD, SD/VT and control groups. Because the majority of VT patients report improvement of their voice symptoms after alcohol intake, we predict that at least 60% (12 patients) of recruited SD/VT group will also be ethanol-responsive. To assure homogeneity between patient populations, we will carefully match SD and SD/VT patients according to their report of alcohol effects, in addition to their age, gender and an SD type match. A total of 60 subjects will undergo 2-hour scanning session for the studies in Specific Aim #1.

For all studies in Specific Aim #2, we will recruit 25 ethanol-responsive SD and SD/VT patients. We estimate that 12 ethanol-responsive patients per group, who participated in the studies in Specific Aim #1, will also participate in the studies in Specific Aim #2. Thus, this will require us to recruit additional 13 SD and 13 SD/VT patients for the proposed studies in Specific Aim #2. A total of newly recruited patients will be 26. The patients will participate in the fMRI studies of this Specific Aim according to the following schedule:

- (1) Because the 12 patients/group, who already underwent neuroimaging studies in Specific Aim #1, will not need a pre-treatment baseline scanning session, they will only complete two 2-hour post-treatment scans with sodium oxybate and botulinum toxin + sodium oxybate, respectively;
- (2) the remaining 13 patients/group will complete three 2-hour scanning sessions, which will include one pre-treatment baseline scan and two post-treatment scans with sodium oxybate and botulinum toxin + sodium oxybate, respectively.

A total number of subjects recruited for studies under both Specific Aims will be 86.

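### The stated Aim 2 group model has no pre/post session factor and no group factor, so as written it tests neither the sodium oxybate change nor the SD/VT versus SD difference; the mixed source of the baseline scan needs a sensitivity analysis.

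*Combined protocol and SAP*

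**What the plan says.** Section 2.3.1 says that post-treatment scans will be compared with pre-treatment scans "to identify differences in brain activation abnormalities due to the effects of sodium oxybate treatment". The sample-size paragraph of that section sizes the study for this before/after change: 22 per group for 80% power at 0.025, with 25 recruited.

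The group analysis in the same section reads: "a two-way ANOVA will be conducted with subject as a random factor and task as fixed factor". A conjunction analysis then identifies "common and distinct regions of activation within the patient group during task production in the pre- and post-treatment fMRI sessions". Section 2.3.2 applies the same pipeline to the combined sodium oxybate and botulinum toxin study. For comparison, the group analysis in section 1.3.1 is a "three-way analysis of variance (ANOVA) with subject as a random factor and the task and group as fixed factors".

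The Specific Aims page and section 2.1 give the Aim 2 hypothesis: sodium oxybate modulates abnormal activation more in SD/VT than in SD.

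On the baseline scan, section 2.3.1 describes two sessions for every patient and the order "Following the initial (baseline) fMRI session, patients will receive an individualized tolerable and efficacious single dose of sodium oxybate". Protection of Human Subjects 1.a instead estimates that 12 patients per group carry over from Aim 1. These patients, "who already underwent neuroimaging studies in Specific Aim #1, will not need a pre-treatment baseline scanning session", complete only the two post-treatment scans. The other 13 per group have their own pre-treatment scan. No section bounds the time from baseline scan to dose.

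**The concern.** With no control condition, the pre/post change is the only evidence on the drug effect, and the SD/VT versus SD difference in that change is the Aim 2 hypothesis. A model with subject and task estimates how activation varies across tasks. It does not estimate how activation changes between sessions, or whether that change differs by group. The analyst would have to choose the deciding contrast after the data are in hand.

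The baseline source is a second, smaller matter. If scans from the Aim 1 visit differed from dedicated Aim 2 baselines for reasons unrelated to the drug, the difference would enter the pooled change in Study 2.3.1 and be read as drug effect. The plan has no step that would show this.

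**Working it through.** **A. What the named factors can test**

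1. Study 1.3.1: subject + task + group is called three-way, so subject is counted as a factor.
2. Study 2.3.1: two-way, with subject and task named. On the same count, both places are taken. Session (pre/post) and group (SD, SD/VT) are absent.
3. The reference back to 1.3.1 in the Aim 2 analysis concerns the first-level regression. The 1.3.1 group model has no session factor either.
4. The conjunction compares thresholded maps. A region above threshold before and below it after is classed as distinct, whether or not the change itself is significant. It gives no estimate of change.
5. The Aim 2 hypothesis is a difference between two changes, (post − pre) in SD/VT minus (post − pre) in SD. That is a session-by-group interaction, and no such term is named.

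**B. The scan counts (Protection of Human Subjects 1.a)**

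- Carried over: 0.60 × 20 = 12 per group. Dedicated baseline: 25 − 12 = 13 per group.
- Newly recruited: 2 × 13 = 26. Total: 3 × 20 + 26 = 86. All the plan's figures reproduce.
- Share of Study 2.3.1 changes resting on an Aim 1 scan: 12/25 = 24/50 = 48%.

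**C. What a shift would do**

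The documents give no size for a shift s specific to Aim 1 baselines, so s is an assumption, in SD units of the change score. The pooled change in a group moves by (12/25)s = 0.48s, or 0.048 SD for each 0.1 SD. In a simulation with no drug effect (n = 25, pooled paired t-test, two-sided 0.025, 200,000 runs), the rejection rate is:

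| s | bias in pooled change | rejection rate |
|---|---|---|
| 0 | 0 | 2.5% |
| 0.25 | 0.12 | 4.8% |
| 0.5 | 0.24 | 11.9% |
| 1.0 | 0.48 | 40.6% |

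**D. What the added analyses can resolve**

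The plan's 22 per group cannot be reproduced, because no SD of the change is given. Solving backwards (paired noncentral t, two-sided 0.025 assumed because sidedness is not stated for Aim 2), 80% power at n = 22 implies dz = 0.70. Power at n is P(T > t(0.9875; n−1)) with noncentrality 0.70√n:

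- n = 25: 85.8%
- n = 13 (dedicated baselines alone): 50.7%

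The source comparison is a two-sample t on change scores with equal variances and noncentrality δ/√(1/n₁ + 1/n₂). The shift detectable with 80% power is:

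- 12 vs 13, within a group: 1.31 SD (97.5% interval half-width 0.96 SD)
- 24 vs 26, groups pooled: 0.90 SD (half-width 0.65 SD)

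For s = 0.5 the within-group comparison has about 14% power. By the same formula, the session-by-group test with 25 vs 25 has 80% power for a difference in change of 0.90 SD.

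All of these figures are for a single scalar change score, such as one region, not for voxelwise-corrected maps.

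**The case against.** The strongest reply is that a paired pre/post comparison is plainly intended. The pilot in section 2.2.2 used a two-tailed paired t-test on active-voxel counts, section 2.3.1 says the scans will be compared, and the sample size is for a before/after change. Pre and post might also be coded as levels of task. This is a grant-style plan in which some detail can be left out. All of that is fair, and a reader should not infer that the investigators overlooked the comparison. But the section names a specific model, and followed as written it does not contain the comparison. Coding session inside task is not stated and would still leave out group.

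On the baseline source, a reader might infer that reused scans are older or otherwise different and that the result is therefore biased. The documents do not support this. Scanner, tasks and trial counts are the same, patients must be symptomatic at the end of their botulinum toxin cycle, and the Timetable runs the two Aims in parallel. Parallel running does not bound the interval, but it removes any presumption of a long one. Nor is the dedicated set a clean reference: an individualized dose follows its baseline scan too, and the pilot describes stepwise dosing ("It was increased individually every two weeks"), so a gap is possible there as well. Baseline source is also confounded with recruitment cohort.

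A smaller reused share might be read from section 2.3: "We estimate that 60% of ethanol-responsive patients per group, who participated in the studies in Specific Aim #1, will also participate". Taking 60% of about 12 ethanol-responsive patients gives about 7 per group. That needs 2 × (25 − 7) = 36 new patients and 60 + 36 = 96 in total, against the stated 26 and 86. The reading is not tenable.

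**Conclusion.** The main point stands and should be corrected. The Aim 2 group model in section 2.3.1, and through it section 2.3.2, has no session term and no group term. As written, it tests neither the pre/post change nor the greater modulation expected in SD/VT. This rests on the printed factor list and on the plan's own naming of the Aim 1 model; it needs no numerical assumption.

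The baseline-source point stands only as a reason for a low-cost sensitivity analysis. Reuse of the Aim 1 scan is implied rather than spelled out: no other pre-treatment scan is described for those patients. The 48% share is an estimate, not a ceiling, and it applies to Study 2.3.1 only. For Study 2.3.2 the plan expects to replace about 60% of patients (0.60 × 25 = 15 per group), so the mix there will differ. No shift is shown, and its size cannot be derived from the documents.

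That the design is uncontrolled is a further limit. It would remain even if all 25 patients had dedicated baselines.

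**What to change.** 1. In section 2.3.1, replace the two-way model with one that has subject (random), task, session (pre, post) and group (SD, SD/VT). Test the session effect within each group and the session-by-group interaction. Keep the conjunction as descriptive. Apply the same structure to Study 2.3.2 with its own session levels.
2. Record the interval from baseline scan to dose, and the time since the last botulinum toxin injection at each scan, for every patient. Report the Study 2.3.1 change by baseline source, with intervals, as a prespecified sensitivity analysis. State in advance that a non-significant source difference is not evidence of no shift.
3. Reconcile section 2.3 with Protection of Human Subjects 1.a: say who has a new baseline scan and who uses the Aim 1 scan, and give one expected number.
4. State in the report that the uncontrolled pre/post change cannot by itself separate drug effect from repeat-scan or time effects.

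The cost is a rewritten model statement, a few recorded dates and one subset analysis, with no added scans or patients. The drawback is precision, as computed above: the source analysis can reveal only a large shift, and the session-by-group test itself is well powered only for a difference of about 0.9 SD.

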2.2 Justification and Feasibility

2.2.1 Review of Relevant Literature. A long-standing observation in patients with primary dystonias, myoclonus and tremor is the improvement of their symptoms with ethanol ingestion. This feature led to recent explorations of sodium oxybate (Xyrem®), which mimics the therapeutic effects of ethanol, as an alternative treatment option for patients with ethanol-responsive movement disorders. Sodium oxybate is chemically identical to gamma-hydroxybutyric acid (GHB), a naturally occurring inhibitory neurotransmitter (Waszkielewicz and Bojarski, 2004). When ingested orally, sodium oxybate is quickly absorbed, crosses the blood-brain barrier and is converted into gamma-aminobutyric acid (GABA) within the brain (Crunelli et al., 2006). In 2002, the FDA approved Xyrem® for the treatment of cataplexy in narcoleptic patients and instituted the Xyrem Success Program® (xyrem.info/healthcare-professionals). The Xyrem Success Program® is a central registry that controls the distribution and administration of Xyrem® (Fuller De Fau - Hornfeldt et al., 2004). Physicians who prescribe Xyrem®, and all patients who receive the drug are registered with the program. After a prescription is written, the central pharmacy contacts the patient and sends the drug directly to the patient. Follow-up phone calls to the patient and regular contacts with the prescribing physicians have ensured that nearly 10,000 patients have received the drug in the United States without known episodes of drug diversion or illicit use.

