Recent tolerability and efficacy trials of sodium oxybate in patients with ET, myoclonus-dystonia and post-hypoxic myoclonus have established satisfactory tolerability and improvement of disorder symptoms over 50% as measured by blinded videotape review ([name] et al., 2005a; [name] et al., 2005b; Arpesella et al., 2009). Our preliminary data further demonstrate that sodium oxybate significantly improves symptoms of SD and VT, with SD/VT patients receiving greater benefits compared to SD patients. Patients with movement disorders usually take 1-2 gm of the drug given three times daily compared to patients with narcolepsy, who take between 4.5 and 9 gm of the drug at night ([name] et al., 2005a; [name] et al., 2005b; Arpesella et al., 2009). Sodium oxybate works quickly, within 45 minutes of oral administration and its effects are visible in the office. Each dose typically lasts 3½-4 hours. Possible side effects include dose-dependent sedation and dizziness, which, however, have marked individual variability. In summary, sodium oxybate may hold promise of a potentially new treatment option for SD and SD/VT, especially for those who have limited symptom improvement following botulinum toxin injections.

2.2.2 Preliminary Data.

I. Sodium oxybate is effective and well tolerated in SD and SD/VT patients. In a pilot study, we evaluated 2 patients with SD and 4 patients with SD/VT. All patients were symptomatic at the time of examination. Three patients were treated with botulinum toxin injections with the last injection received at least 3 months prior to the study participation; botulinum toxin treatment in the other 3 patients was not successful. All patients reported significant relief of their symptoms with ingestion of alcohol.

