5. To avoid the possibility of confounding effects of drugs acting upon the central nervous system, all study participants will be questioned about *any* prescribed or over-the-counter medications as part of their initial intake screening (see **Appendix 1**). Those patients who receive medication(s) affecting the central nervous system (except sodium oxybate as part of the studies under Specific Aim #2) will be excluded from the study.
6. The patients will be asked whether they have undergone any head and neck surgeries, particularly any brain surgery and laryngeal surgeries, such as thyroplasty, laryngeal denervation, and selective laryngeal adductor denervation-reinnervation (see **Appendix 1**). Because both brain and laryngeal surgery may potentially lead to the brain structure and function re-organization, all patients with history of brain and/or laryngeal surgery will be excluded from the study.
7. Subjects who have tattoos, ferromagnetic objects in their bodies (e.g., implanted stimulators, surgical clips, prosthesis, artificial heart valve, etc.) that cannot be removed for the purpose of study participation.

Subjects accepted into the study will require up to four visits for patients and up to two visits for healthy controls, including one screening visit (intake questionnaire, self-screening questionnaire, voice and speech recording, nasolaryngoscopy, neurological exam) and one to three scanning session depending whether healthy control or patient. Time commitment for the screening visit may be up to 3 hours for patients and 1 hour for healthy volunteers; fMRI, MRI and DTI will be combined into the same scanning session of up to 2 hours. Scanning sessions will be scheduled according to the treatment schedule.

b. Sources of Material. Every effort will be made to respect and maintain the confidentiality of study participants according to the current legal requirements and as required by the Federal Privacy Act. The TBR Research Associate will be directly involved in the maintaining of subject databases, ensuring that strict standards of confidentiality are upheld at all times. Only the research team will have access to the research

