data. Subject identifying information will be removed from neuroimaging data, nasolaryngoscopy, voice and speech recordings. A unique research code will be assigned to all data for confidentiality purposes. The list linking the codes to the subjects will be stored on the PI's password-secured computer. Only the PI will have an access to the list linking the code to the subject. The cross-reference will be available only to the investigators associated with this project.

Hard copies of the results of the physical exam, medical history, questionnaires and evaluations will be kept in the secured cabinets and password-protected computers located in the PI's office.

Neuroimaging data will be kept on the secured password-protected servers and image processing workstations in the PI's laboratory. Data will be backed up on the laboratory's protected storage servers.

All digitalized data from patients' nasolaryngoscopy, voice and speech recordings will be kept on the password-protected server accessible only by the members of the research team.

c. Potential Risks. Participation in these studies will entail minimal risk.

1. There may be some discomfort associated with *fiberoptic nasolaryngoscopy*. Prior to nasolaryngoscopy, the decongestant may be applied through the nares to widen the nasal passages. The subjects may experience mild discomfort in the nose or pharynx. The taste may be unpleasant. During the procedure, most people have a vague awareness that something is in their nose and brief feelings of nasal pressure or an urge to sneeze. When the nasolaryngoscope reaches the back of the nose, subjects may feel a slight pinch for a few seconds. Sometimes, the examination triggers a cough or gag, which stops when the nasolaryngoscope is repositioned. Discomfort is more common in people with a narrow nasal passages or a deviated septum. In these cases, a smaller nasolaryngoscope will be used. Problems that sometimes occur with nasolaryngoscopy may include coughing, gagging, vomiting, or a slight drop in pressure causing faintness. In these cases, the examination can be stopped, restarted, cancelled, or re-scheduled. Other problems that may occur but are rare include a nosebleed, choking, infection, spasm of the larynx, or an allergic reaction. Sudden or unexpected head movement not requested by the examiner during the nasolaryngoscopy can cause bleeding or other injury. After the examination, some people may have a mild sore throat for a few hours.

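### The risk and safeguard sections omit sodium oxybate, although the protocol names sedation and dizziness as possible effects, and no check is set before a dosed outpatient leaves

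*Combined protocol and SAP*

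**What the plan says.** The risk conclusion in Protection of Human Subjects 1c applies to all the studies: "Participation in these studies will entail minimal risk". Three numbered items follow: nasolaryngoscopy, fMRI/MRI/DTI and loss of data. Section 2b has one headed paragraph on the endoscope and one on the scanner, then text on pregnancy and on fatigue from the vocal tasks. Section 3 says that patients in the sodium oxybate study may benefit directly.

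The drug's possible harms appear only in the background, in 2.2.1: "Possible side effects include dose-dependent sedation and dizziness, which, however, have marked individual variability". The same paragraph says that a dose typically lasts 3.5 to 4 hours.

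In Study 2.3.1, after the baseline scan, "patients will receive an individualized tolerable and efficacious single dose of sodium oxybate, given orally in the office". Symptoms are evaluated and videotaped one hour later, and the second scan follows at once. In Study 2.3.2, patients who benefit from botulinum toxin take their sodium oxybate dose three times daily from the end of 2.3.1 until 2.3.2 ends, and have a third scan at least 14 days after the injection. That section also gives side effects of the injection: breathiness in more than half of patients and difficulty swallowing liquids in 14%. All subjects are outpatients (1a).

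**The concern.** The risk section goes down to small matters such as an unpleasant taste or a mild sore throat after endoscopy, so silence on the study drug is not explained by brevity. The drug is weighed as a possible benefit but not as a risk, and no written safeguard is specific to it, either on the day of the office dose or during use at home. What is at stake is the safety of sedated or dizzy outpatients and the basis for the minimal-risk statement. No statistical analysis is affected.

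**Working it through.** **Coverage of sections 1c and 2b**

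| Exposure | Listed as a risk in 1c | Safeguard in 1c or 2b | Effects named elsewhere |
|---|---|---|---|
| Nasolaryngoscopy | yes | yes (2b) | – |
| fMRI/MRI/DTI | yes | yes (2b) | – |
| Loss of data | yes | yes (1c, coding and encryption) | – |
| Sodium oxybate | no | no | sedation, dizziness (2.2.1) |
| Botulinum toxin | no | no | breathiness, dysphagia (2.3.2) |

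**Number exposed**

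- The plan's own total first. Section 1a gives 3 groups of 20 for Aim 1 and 13 new patients in each of 2 groups for Aim 2: 3 × 20 + 2 × 13 = 60 + 26 = 86, as stated.
- Dosed in Study 2.3.1: 2 × (12 + 13) = 2 × 25 = 50.
- Continuing into Study 2.3.2 (about 40% benefit from botulinum toxin): 0.40 × 50 = 20.
- Section 2.3.2 replaces the other 60% or so with new patients: 0.60 × 50 = 30. It says that all patients in that study receive both treatments, so up to 20 + 30 = 50 would take the drug there.
- Ever exposed if those replacements are recruited: 50 + 30 = 80, against the 50 implied by 1a. Recruitment would be 86 + 30 = 116, against the stated 86.

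Sections 1a and 2.3.2 therefore disagree on replacement. Exposure is 50 on one reading and about 80 on the other.

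**Time from dose to end of scan**

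- Evaluation at 1 hour (2.3.1), then a scan of up to 2 hours (1a): 1 + 2 = 3 hours, ignoring the time the evaluation takes.
- Stated duration of a dose (2.2.1): 3.5 to 4 hours.
- Difference: 3.5 − 3 = 0.5 hour to 4 − 3 = 1 hour. It is longer if the scan is shorter.

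A patient can thus finish the last scheduled procedure while the dose is, by the protocol's own figure, still active. The one-hour evaluation concerns the patient's symptoms; no check of alertness or balance is described.

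**The case against.** The protocol does give reasons for confidence. The office dose is to be individualized and tolerable. Of the pilot it reports: "Sodium oxybate was well tolerated by all patients without tolerance and rebound". Section 2.2.1 adds satisfactory tolerability in trials of other movement disorders, FDA approval, nearly 10,000 patients treated, and daytime doses below the nightly narcolepsy dose. Alcoholism, drug dependence and other drugs acting on the central nervous system are exclusions (the last to avoid confounding). A scan session ends if a risky condition develops, and subjects may contact the principal investigator with questions. The registry program provides "Follow-up phone calls to the patient and regular contacts with the prescribing physicians", though its results are reported as absence of diversion or illicit use. The botulinum toxin injections may be the patients' usual care.

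All of this stands, and it may support a low risk rating. None of it lists the effects as study risks or says what is checked before a dosed patient leaves. Pilot doses were adjusted every two weeks "until a dose was achieved that improved symptoms without undesirable side effects", whereas the visit plan in 1a shows no dose-finding visit.

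A reader might infer more than the documents support:

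- *That the label contradicts the named side effects.* Possible sedation and dizziness do not by themselves exceed minimal risk, and the documents set no threshold.
- *That patients are sent home sedated.* The 3.5 to 4 hours is the duration of a dose, not of sedation, and the time of leaving is not given.
- *That patients taking the drug at home are not seen again.* Section 2a schedules no follow-up hospital visits unless needed, but Study 2.3.2 has its third scan. Only the interval before it lacks a stated check.
- *That six pilot patients are too few to support the label.* The protocol does not rest tolerability on the pilot alone, and it reports no event count from which to compute a limit.
- *That patients would not be told.* Consent pages are not available and are not judged. Section 2a says that risks are described at first contact.

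**Conclusion.** The point holds as an omission. Sections 1c and 2b leave out sodium oxybate and the botulinum toxin effects that the protocol gives elsewhere, and the minimal-risk statement is made without weighing them. It concerns 50 outpatients dosed in Study 2.3.1, and three-times-daily use by about 20 to 50 patients in Study 2.3.2. The upper figure, and the 80 ever exposed, assume that the replacements in 2.3.2 are recruited and follow the same regimen. The gap of about 0.5 to 1 hour between the end of scanning and the end of a dose assumes a full 2-hour scan; it shows why a check is sensible and does not measure harm. The change should be made, as it is a cheap safety step at a visit that already exists.

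**What to change.** 1. In 1c, add sodium oxybate with sedation and dizziness, and for Study 2.3.2 add the breathiness and dysphagia that the protocol reports after botulinum toxin.
2. Re-justify or revise the minimal-risk statement for Specific Aim 2.
3. In 2b, add a safeguard paragraph, referenced from 2.3.1 and 2.3.2. A study clinician checks for significant sedation and dizziness, and records their absence, before an office-dosed patient leaves. Patients taking the drug three times daily get a clinical contact for these effects.

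When the section is revised, state whether the replacements in 2.3.2 will be recruited, so that the number exposed is clear.

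The cost is a few short paragraphs and a brief recorded check at an existing visit. Some patients will stay a little longer, and the minimal-risk label may not stand.
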